CharitéCentrum für Human- und Gesundheitswissenschaften

Charité | [name]

Institut für Klinische Pflegewissenschaft

[name]
<https://klinische-pflegewissenschaft.charite.de/>

[contact]
Email: [contact]

Study Protocol with Statistical Analysis Plan (SAP)
**Comparison of two skin protection regimes for the Prevention of
Incontinence-associated Dermatitis in geriatric care: An exploratory trial
(PID)**

Study Code: PID

NCT Number: NCT05403762

Study Protocol V1.1, 15 June 2022; SAP V4, 17 April 2025

INVESTIGATORS	
[name]. rer. cur. [name] Charité – Universitätsmedizin Berlin Institute for Clinical Nursing Science [name] Email: [contact]	Priv.-Doz. Dr. rer. cur. [name] Charité-Universitätsmedizin Berlin Research Group Geriatrics [name] Email: [contact]
PROTOCOL DEVELOPMENT	SPONSOR
[name] [name] [name] [name] [name]. rer. cur. [name] Priv.-Doz. Dr. rer. cur. [name]	Charité – Universitätsmedizin Berlin
FUNDING	

Bundesministerium für Bildung und Forschung (BMBF), FKZ 01KG2020

I. SUMMARY

Title of the clinical study	Comparison of two skin protection regimes for the P revention of I ncontinence-associated D ermatitis in geriatric care: an exploratory trial (PID)
Funding	Bundesministerium für Bildung und Forschung (BMBF), FKZ 01KG2020
Investigators	[name]. rer. cur. [name] Priv.-Doz. Dr. rer. cur. [name]
Study period	July 2022 to January 2024
Study design	Randomized controlled, parallel group, three-arm, assessor-blinded exploratory trial
Number of subjects	
 To be assessed for eligibility (n = 500 subjects) To be allocated to trial (n = 210 subjects; n = 70 per study arm) To be analyzed (n = 180 subjects; n = 60 subjects per study arm)
Objectives	The primary research objective is to compare the incidence of incontinence-associated dermatitis (IAD) in two intervention groups and one control group and to estimate effect sizes for a possible subsequent confirmatory randomized controlled trial (RCT). Additional objectives are to test the feasibility of conducting a confirmatory RCT to prevent IAD and to evaluate the feasibility of measuring the Core Outcome Domains for IAD trials.
Outcomes	
 IAD incidence Erythema Erosion Maceration IAD-related pain IAD-related itch Satisfaction with treatment Willingness to participate Retention Adherence to prescribed intervention Adverse Events (AEs) and Serious Adverse Events (SAEs) according to the definition of the EU regulation 2017/745 Medical Device Regulation (MDR) Article 2 (57) and (58) Incidents and Serious Incidents according to the definition of the EU regulation 2017/745 MDR Article 2 (64) and (65)

Eligibility criteria	
Institutional Level
 
Inclusion criteria:
 
 • Nursing home, geriatric hospital or hospital with geriatric ward(s) in the federal state of Berlin • Expression of a clear commitment to apply the study related procedures • Willingness to regularly allow study related trainings (on site at the nursing home/ hospital, conducted by study personnel) and to allow and ensure the participation by a sufficient number of employees • Agreement that study-related documents, such as diaries, will be completed daily by involved caregivers to ensure compliance and that study personnel may review these documents on a regular interval • Commitment to adhere to the trial procedures 
Exclusion criteria:
 
 • Any circumstance that makes it unfeasible to conduct the study in the nursing home/ hospital in accordance to the study protocol 
Participant Level
 
Inclusion criteria:
 
 • Geriatric patients or residents (≥ 65 years) staying/living in one of the participating institutions • being incontinent of urine and stool • Expected minimum length of stay of 14 days • Intact skin with no clinical signs of IAD 
OR
 
intact skin with early clinical signs of IAD but without clinical signs of infection (GLOBIAD category 1 A)
 
 • Written informed consent 
Exclusion criteria:
 
 • Residents/patients at the end of life • Residents/Patients with skin loss due to IAD (GLOBIAD category 2 A) and/or signs of clinical infection in the IAD area (GLOBIAD category 1 B or 2 B) • Any other skin condition or wounds (at investigational areas of the skin) requiring additional treatment (including but not limited to pressure ulcers, intertrigo, infection) • Known hypersensitivity or allergy to silicones and/or topical leave-on products
----------------------	------------------------------------------------------------------------------------------------------------------------------------------------------------------------------------------------------------------------------------------------------------------------------------------------------------------------------------------------------------------------------------------------------------------------------------------------------------------------------------------------------------------------------------------------------------------------------------------------------------------------------------------------------------------------------------------------------------------------------------------------------------------------------------------------------------------------------------------------------------------------------------------------------------------------------------------------------------------------------------------------------------------------------------------------------------------------------------------------------------------------------------------------------------------------------------------------------------------------------------------------------------------------------------------------------------------------------------------------------------------------------------------------------------------------------------------------------------------------------------------------------------------------------------------------------------------------------------------------------------------------------------------------------------------------------------------------------------------------------------------------------------------------------------------------------------------------------------------------------------------------------------------------------------------------------------------------------------------------------------------------------------------------------------------------------------------------------------------------------------------------------------------------------------------------------------------------------------------------------------------------------------------------------

	
 • Topical treatments in the IAD area.
Intervention(s)	
 • Experimental intervention I: Standardized mild skin cleansing regimen and daily topical application of a film-forming skin protectant at the exposed skin areas. • Experimental intervention II: Standardized mild skin cleansing regimen and daily topical application of a hydrophobic skin protectant at the exposed skin areas. • Control intervention: Standardized mild skin cleansing regimen without application of an additional skin protectant.
Duration of treatment	
 • Duration of intervention per patient: 14 days • Follow-up per patient: 14 days
Statistical methods	
Efficacy: The endpoints will be compared descriptively between the three groups. No confirmatory statistical tests will be conducted.
 
Description of the primary efficacy analysis and population: The intention-to-treat (ITT) principle will be applied, including all subjects that were allocated to a study group.
 
Safety: AEs, SAEs, incidents and serious incidents will be listed per patient and for the total trial.

II. TABLE OF CONTENTS

I.	Summary	2
II.	Table of contents	5
III.	Tables and Figures	8
IV.	List of Abbreviations.....	9
V.	Administrative Information	10
1.	Introduction	12
1.1	Background and rationale	12
1.2	Objectives	13
1.3	Trial design.....	13
2.	Methods: Participants, interventions, and outcomes	14
2.1	Study setting	14
2.2	Eligibility criteria	14
2.2.1	Institutional level.....	14
2.2.2	Resident/patient level	14
2.3	Interventions	15
2.3.1	Qualitative interview part	18
2.3.2	Criteria for discontinuing	18
2.4	Education	19
2.4.1	Trainings	19
2.4.2	Materials.....	19
2.5	Strategies to improve compliance and adherence to the study protocol	20
2.6	Concomitant care and interventions	20
2.7	Outcomes and variables	20
2.7.1	Initial skin assessment.....	26
2.7.2	Mexameter measurement	26
2.7.3	Resident/Patient reported outcome measures	26
2.7.4	Participants Timeline.....	28
2.8	Sample Size	30
2.8.1	Whole trial.....	30

2.8.2	Interview Part	30
2.9	Recruitment	30
2.9.1	Institutional Level	30
2.9.2	Participant Level	30
3.	Methods: Assignment of interventions	31
3.1	Sequence generation	31
3.2	Allocation concealment mechanism	31
3.3	Blinding	31
4.	Methods: Data collection, management, and analysis	32
4.1	Data collection methods	32
4.1.1	Skin assessment	33
4.1.2	Skin measurements	33
4.1.3	Other trial data	33
4.2	Data management	36

1. INTRODUCTION

1.1 BACKGROUND AND RATIONALE

Incontinence-associated dermatitis (IAD) is an unwanted skin condition which is common in incontinent individuals. It is an inflammatory skin response due to repeated or prolonged contact with urine and/or stool [1, 2]. It can occur throughout the lifespan, thus it is present in babies and young children ("diaper dermatitis") as well as in the older individuals [1].

The prevalence of incontinence rises with increasing age [3]; therefore, IAD is more common in the aged population. IAD prevalence is 3% to 23% in long-term geriatric care and 15% to 40% in acute care settings [4]. A representative prevalence study in institutional geriatric long-term care facilities showed an IAD prevalence of 35.4% [5, 6]. Thus, around one in three residents was affected by some form of IAD.

Clinically, IAD is manifested by skin redness, vesicles, nodular thickening and maceration of the tissue as well as defects of the skin up to the loss of the upper skin layers. For those affected, this can be a physical as well as psychological burden. In addition to pain, burning, and itching, IAD is associated with an increased risk of secondary infections and the development of pressure ulcers (PUs) [7, 8]. As a result of these changes, affected individuals may also suffer from a reduced quality of life, for example, through a loss of independence, reduction of social activities, or poor sleep due to IAD-related pain or itch [6, 9, 10].

With approximately 80%, the majority of residents in geriatric long-term care facilities, as well as a high proportion of geriatric patients in acute care settings, are affected by one form of incontinence and are therefore at potential risk of developing IAD [11-13]. If adequate preventive measures are taken at an early stage, IAD might be avoided. However, the high prevalence of IAD in these settings indicates that current prevention strategies are not optimal. Due to a lack of knowledge, the current nursing practices in the context of IAD prevention are mainly influenced by individual traditions and personal preferences and are not evidence-based [14]. At the same time, a clear need for support as well as assistance is expressed on the part of nurses and other caregivers in order to be able to perform an efficient and effective IAD prevention [15]. Therefore, it is an important aim to close existing evidence gaps in this area to support nurses and other caregivers with a solid scientific base for IAD prevention. The planned trial aims a direct comparison of the two most important skin protection product categories in the form of an explorative randomized controlled trial (RCT), taking core outcomes for IAD research into account.

1.2 OBJECTIVES

The primary research objective is to compare the incidence of IAD in the intervention and control groups to estimate effect sizes for a possible subsequent confirmatory RCT. Another objective is to evaluate the feasibility of the planned interventional skin care regimen in geriatric populations. This will be the first time, the recently developed set of IAD-specific outcomes (CONSIDER) [16] will be used and evaluated in the context of a clinical trial. This Core Outcome Set (COS) is intended to improve the comparability and pooling of future data from different studies in the field of IAD research to provide a basis for evidence-based health care.

The trial will answer the following research questions:

- What are the effect sizes of the outcomes?
- Is the implementation of a standardized skin protection regime for the prevention of IAD feasible in geriatric hospital wards and nursing homes?
- Does the implementation of a standardized skin protection regime for the prevention of IAD reduce itch and IAD-related pain?
- Is the measurement of Core Outcome Domains for IAD trials feasible?

1.3 TRIAL DESIGN

Randomized controlled, parallel group, three-arm, assessor-blinded exploratory trial

2. METHODS: PARTICIPANTS, INTERVENTIONS, AND OUTCOMES

2.1 STUDY SETTING

The study will be conducted in geriatric hospitals/geriatric wards of participating hospitals and in institutional long-term care facilities of the federal state of Berlin, Germany.

2.2 ELIGIBILITY CRITERIA

2.2.1 INSTITUTIONAL LEVEL

Inclusion criteria:

- (1) Nursing home, geriatric hospital or hospital with geriatric ward(s) in the federal state of Berlin
- (2) Expression of a clear commitment to apply the study related procedures
- (3) Willingness to regularly allow study related trainings (on site at the nursing home/ hospital, conducted by study personnel) and to allow and ensure the participation by a sufficient number of employees
- (4) Agreement that study-related documents, such as diaries, will be completed daily by involved caregivers to ensure compliance and that study personnel may review these documents on a regular interval
- (5) Commitment to adhere to the trial procedures

Exclusion criteria:

- (1) Any circumstance that makes it unfeasible to conduct the study in the nursing home/ hospital in accordance to the study protocol

2.2.2 RESIDENT/PATIENT LEVEL

Inclusion criteria:

Geriatric patients (≥ 65 years) admitted to geriatric wards of participating hospitals or residents of participating nursing homes can be included if the following criteria are met:

- (1) Being incontinent of urine and stool
- (2) Expected minimum length of stay of 14 days
- (3) Intact skin with no clinical signs of IAD

OR

Intact skin with early clinical signs of IAD (erythema) but without clinical signs of infection (GLOBIAD category 1 A)

- (4) Written informed consent (by legal representative, if required)

Exclusion criteria:

- (1) Residents/patients at the end of life
- (2) Residents/Patients with skin loss due to IAD (GLOBIAD category 2 A) and/or signs of clinical infection in the IAD area (GLOBIAD category 1 B, category 2 B)
- (3) Any other skin condition or wounds (at investigational areas of the skin) requiring additional treatment (including but not limited to pressure ulcers, intertrigo, infection)
- (4) Known hypersensitivity or allergy to silicones and/or topical leave-on products
- (5) Topical treatments in the IAD area.

2.3 INTERVENTIONS

Included participants of all three groups receive a standardized skin cleansing regime consisting of cleansing of the skin with water and the addition of a mild cleansing product. Cleansing is done using disposable washing mitts. To remove possible residual stool from the skin, an additional skin oil can be used. After subsequent gentle drying of the skin, elastic disposable breathable incontinence pants are put on. This is considered as 'standard incontinence care'. In order to ensure the greatest possible standardization and uniformity, the same predefined products and procedures are used for all participants. The required products for the participants will be provided by the investigators and are listed in Table 1.

After baseline visits, included residents/patients will be randomly assigned on Day 0 to one of the following three study arms:

- **Study arm 1 (Experimental intervention I):** Standard incontinence care with additional daily topical application of a film-forming leave-on skin protectant (ESENTA™ Hautschutz Spray) that builds a protective layer on the surface of the skin
- **Study arm 2 (Experimental intervention II):** Standard incontinence care with additional daily topical application of a lipophilic leave-on skin protectant (Hydrophobes Basisgel DAC) that forms a hydrophobic physical barrier on the skin
- **Study arm 3 (Control group):** Standard incontinence care alone, no additional intervention in the control group

The interventions are described in detail according to the template for intervention description and replication (TIDieR) checklist [17] in Table 1. The items 10 and 12 do not apply for study protocols and are therefore not listed in the table [17].

Table 1: Description of interventions according to the template for intervention description and replication (TIDieR) [17].

Item	Experimental intervention I	Experimental intervention II	Control group
1. Brief name	Film-forming leave-on skin protectant for IAD prevention	Hydrophobic leave-on skin protectant for IAD prevention	No skin protectant
2. Rationale	Film-forming topical leave-on products are widely used to protect the skin from irritants including urine and/or stool in incontinent patients [18, 19]. Whether film-forming products are better than hydrophobic ointments/emulsions or no skin protectants is unclear.	Monophasic or biphasic hydrophobic (emulsions) topical leave-on products are widely used to protect the skin from irritants including urine and/or stool in incontinent patients [18]. Whether hydrophobic leave-on products are better than film-forming products or no products is unclear.	Most incontinent patients do not receive any topical skin protectant when the skin is intact. The relative and absolute benefit of applying any skin protectant to intact skin of incontinent geriatric patients is unclear.
3. Materials	
- Skin will be cleansed with water and the addition of a mild cleanser (preferably non-alkaline skin cleansers with a pH range similar to normal skin and non-ionic surfactants, e.g. Bübchen Creme Pflegebad, Nestlé Nutrition GmbH, Germany) using disposable wash mitts/cloths (e.g. Waschhandschuh PLUS, Desomed AG, Germany)
 
- A skin oil (perfume-free, dye-free, e.g. Baby Öl, Nestlé Nutrition GmbH, Germany) may be used in addition to remove stool.
 
- ESENTA™ Skin Barrier (ConvaTec Inc., UK) will be applied on clean and dry skin exposed to urine and stool. After application, the solvent evaporates leaving a silicone film on the skin surface.
 
- Elastic disposable breathable incontinence pants are put on (e.g. Seni active classic, TZMO Deutschland GmbH, Germany).
	
- Skin will be cleansed with water and the addition of a mild cleanser (preferably non-alkaline skin cleansers with a pH range similar to normal skin and non-ionic surfactants, e.g. Bübchen Creme Pflegebad, Nestlé Nutrition GmbH, Germany) using disposable wash mitts/cloths (e.g. Waschhandschuh PLUS, Desomed AG, Germany)
 
- A skin oil (perfume-free, dye-free, e.g. Baby Öl, Nestlé Nutrition GmbH, Germany) may be used in addition to remove stool.
 
- Hydrophobes Basisgel DAC will be applied on clean and dry skin. It contains 95% paraffin oil and creates a hydrophobic layer on the skin surface [20].
 
- Elastic disposable breathable incontinence pants are put on (e.g. Seni active classic, TZMO Deutschland GmbH, Germany).
	
- Skin will be cleansed with water and the addition of a mild cleanser (preferably non-alkaline skin cleansers with a pH range similar to normal skin and non-ionic surfactants, e.g. Bübchen Creme Pflegebad, Nestlé Nutrition GmbH, Germany) using disposable wash mitts/cloths (e.g. Waschhandschuh PLUS, Desomed AG, Germany)
 
- A skin oil (perfume-free, dye-free, e.g. Baby Öl, Nestlé Nutrition GmbH, Germany) may be used in addition to remove stool.
 
- Elastic disposable breathable incontinence pants are put on (e.g. Seni active classic, TZMO Deutschland GmbH, Germany).

4. Procedures	After regular skin cleansing in the morning, the skin protectant is applied to dry skin.	After regular skin cleansing in the morning and evening, the skin protectant is applied to dry skin. In addition, the product is reapplied following the skin cleansing after a stool incontinence episode.	After regular skin cleansing, no additional skin protectant is applied.
	Prior to the beginning of the study, ward nurses are educated in interactive face-to-face meetings. Handouts will be provided and posters summarizing the study procedures are placed on the wards. Regular refresher meetings are held every three months under the supervision of the investigators.		

5. Who provides?	Ward nurses who participated in an educational session about this study and the procedures and thus have study-relevant knowledge.		
6. How	
 - After removal of the incontinence briefs, the skin is cleansed and dried. - An oil may be used to remove stool and/or residual products. - The skin protectant is applied to dry skin. According to manufacturer instructions, the spray must be hold approximately 10 cm away from the skin surface. A uniform layer of the product is applied using a sweeping motion over the area to be protected. The film must be completely dry before the person is turned onto their back, new incontinence materials are placed or clothing is put on. - New incontinence pants are put on (if needed from the view of the nurses). 	
 - After removal of the incontinence briefs, the skin is cleansed and dried. - An oil may be used to remove stool and/or residual products. - The skin protectant is applied to dry skin. - New incontinence pants are put on (if needed from the view of the nurses). 	
 - After removal of the incontinence briefs, the skin is cleansed and dried. - An oil may be used to remove stool and/or residual products. - New incontinence pants are put on (if needed from the view of the nurses).
7. Where	In the patient rooms, in or outside of the bed.		
8. When and how much	It is widely assumed that polymeric films protect the skin up to 72 hours [21]. According to manufactures instruction, reapplication of ESENTA™ Skin Barrier (ConvaTec Inc., UK) is recommended every 12 to 72 hours. To ensure sufficient skin protection and to standardize application within this trial, the product will be applied once daily in the morning as a uniform film to cover the exposed skin area.	Because traditional lipophilic leave-on products do not adhere to the skin surface that strongly, it may be removed more easily. To ensure sufficient protection the Hydrophobes Basisgel DAC will be applied twice daily (in the morning and evening) as a thin layer on the skin exposed to urine and stool.	Not applicable
9. Tailoring*	The frequency and intensity of skin cleansing and the application of new incontinence material will be based on the number and intensity of incontinence episodes.		
	Not applicable	The skin protectant will be reapplied in addition after every stool removal from the skin.	Not applicable
11. How well*	Ward nurses are initially trained and retrained after 3 months, after 6 month, and as needed at individual additional meetings. During the study, the nurses continuously document the study related procedures performed (cleansing, use of leave-on products, used materials) in a resident/patient-specific diary. The study personnel check these diaries daily for completeness and consistency to ensure and improve compliance and adherence to the protocol.		

*Item 10 and 12 do not apply for study protocols and are therefore not listed in the table

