Physical function	
 Barthel – Index Score range: 0 to 100 Means 	Day 0	
 Item 1: Feeding (0; 5 or 10 points) Item 2: Bathing (0 or 5 points) Item 3: Personal toilet (0 or 5 points) Item 4: Dressing and undressing (0; 5 or 10 points) Item 5: Controlling bowels (0; 5 or 10 points) Item 6: Controlling bladder (0; 5 or 10 points) Item 7: Toilet use (0; 5 or 10 points) Item 8: Transfer (bed to chair and back) (0; 5; 10 or 15 points) Item 9: Standing up and Mobility (0; 5; 10 or 15 points) Item 10: Ascend and descend stairs (0; 5 or 10 points)
Diarrhoea	
 Interview by study assistant or obtained from medical records 	Day 0	
 Diarrhoea (0) No (1) Yes
Urinary tract infection	
 Interview by study assistant or obtained from medical records 	Day 0	
 Urinary tract infection (0) No (1) Yes

Demographic variables (age, sex, care level,), main medical diseases, medications and, if possible, Barthel-Index scores will be obtained from medical records by trained study assistants. Data regarding incontinence will be obtained from the medical records or if possible via interview of the participants or the responsible caregiver.

A possible cognitive impairment will be rated using the MMSE [29]. Only residents with a score of 24 or higher will receive the questionnaires regarding itch, pain and patient satisfaction. A functional assessment using the Barthel-Index will be conducted by study assistants, if this has not already been done by the nursing home. The Barthel-Index measures physical function related to the daily activities using ten items (e.g. washing and toilet use, eating and mobility or incontinence). Scores ranges from 0 (= very dependent) to 100 (= not dependent) [38].

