7.2 Analyses of endpoints

Because of the exploratory nature of the trial and according to methodological guidance for exploratory trials, a distinction between primary and secondary endpoints is not made [23]. Because the main aim is to prevent IAD, IAD incidence is likely to be considered as a primary outcome in a possible subsequent confirmatory trial and is therefore considered as primary efficacy variable.

For all outcomes, total group differences are reported by the corresponding effect size based on the statistical models as outlines below and corresponding 95% confidence intervals. Relevant timepoints will be Day 6 and Day14. Day0 reports will be presented as is.

The relevant blinded group comparisons are: A vs. B; A vs. C; B vs. C.

For cumulative incidence rates of IAD, Kaplan-Meier Curves will be presented with time ranging from inclusion to IAD onset, i.e. the first occurrence of IAD 2A or 2B. Censoring occurs if patients withdraw from the study before the onset of an IAD or if the study is terminated before IAD onset. Mixed effects Cox regression model (shared frailty model) will be carried out for group comparisons of incidence rates. The latter includes group allocation, sex, setting (nursery home, geriatric hospital ward) and time (continuous) as fixed effects and random intercepts for the ward and the patients. The resulting Hazard ratios for IAD will be presented. Potential non-linear time effects will be explored and modelled using fractional polynomials or splines.

Group differences for categorical, dichotomous responses are calculated by estimating group effects from either generalized linear mixed-effects models (binary logistic) - including particular baseline status (maceration, IAD-related itch), group allocation, sex, setting and time as fixed effects and random intercepts per ward and patients - or nonparametric analysis of longitudinal data depending on the distribution of the data. For the Erosion model, no baseline adjustment is considered due to its presence is an exclusion criterion.

List:

- Erosion (no/ yes)
- Maceration (no/ yes)
- IAD related itch (no/ yes) [only measured if IAD present]
- IAD-related pain (no/yes) [only measured if IAD present]

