7.3 Planned subgroup analyses

Differential treatment effects will be analyzed by including interaction terms for subgroups by intervention group. Prespecified subgroups include sex (male/female) and patients with and without IAD 1A status at baseline. For the subgroup consisting of no initial IAD, a second time-to-event analysis will be realized, using the first occurrence of any IAD category as event and thus including 1A and 1B. Additionally, location (front/back) of IAD and Erosion will be considered for subgroup analyses as well. Parallel to interaction effects estimated marginal treatment effects of the subgroups and 95% CI will be reported.

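### Day 0 diarrhoea is collected before allocation and plausibly prognostic for IAD, but no SAP model uses it, so a chance imbalance between arms would go uncorrected (minor)

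*Combined protocol and SAP*

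**What the plan says.** Protocol 1.1 describes the cause of IAD: "It is an inflammatory skin response due to repeated or prolonged contact with urine and/or stool". Every participant must meet the entry criterion "Being incontinent of urine and stool" (protocol 2.2.2).

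The product regimens differ in how they respond to stool (protocol 2.3, Table 1, items 8 and 9). For the film, "the product will be applied once daily in the morning as a uniform film to cover the exposed skin area", and tailoring of the product does not apply. For the gel there are two scheduled applications a day and, beyond these, "The skin protectant will be reapplied in addition after every stool removal from the skin". Controls receive no protectant.

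Protocol 4.1.3, Table 4, lists a Day 0 item, "Diarrhoea (0) No (1) Yes", with the source given as "Interview by study assistant or obtained from medical records". SAP 4.1 codes it as dm_0120 with Yes, No and Unknown, reported as n (%), and SAP 7.1 restricts baseline variables to description. Protocol 2.3 places randomisation after the baseline visit.

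For the main Cox model, SAP 7.2 states: "The latter includes group allocation, sex, setting (nursery home, geriatric hospital ward) and time (continuous) as fixed effects". Ward and patient enter as random intercepts. The other models use group, sex, setting, time and, where relevant, the outcome's own baseline status. On subgroups, SAP 7.3 states: "Prespecified subgroups include sex (male/female) and patients with and without IAD 1A status at baseline". It adds location (front or back). Randomisation is stratified by sex, with separate lists by setting (protocol 3.1).

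**The concern.** The trial's stated purpose is to estimate effect sizes for a possible confirmatory trial. A baseline variable that bears on the named cause of the main outcome, is fixed before allocation and is already in the database is an obvious candidate for covariate adjustment. Because diarrhoea is neither a stratum nor a covariate, any difference in its frequency between arms passes into the estimated hazard ratios for IAD and into the erosion and maceration contrasts.

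The design also gives a specific reason to look at stool load. Of the two product regimens, only the gel regimen increases with stool episodes, so a film-versus-gel effect that varies with stool exposure is a natural exploratory question. SAP 7.3 does not raise it.

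**Working it through.** **Inputs from the documents.** SAP section 3 reports 220 recruited, so 220 / 3 ≈ 73 per arm (protocol 2.8.1 planned 70 included and 60 analysed). Visits are every two days to Day 14. The main event is the first GLOBIAD 2A or 2B. The plan states no power, effect size, event rate or dropout rate, so it has no figure of its own to reproduce here.

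**Assumptions not in the documents.** Diarrhoea prevalence p of 10% to 30%; hazard ratio for diarrhoea HR_d of 1.5 to 3; product hazard ratio 0.5.

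**Step 1: size of chance imbalance.** For two arms of n = 73, the SD of the difference in prevalence is sqrt(2p(1−p)/n).

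| p | SD | 95% limit (1.96 × SD) | P(a given pair differs by ≥ 10 points) | P(some pair of the three does) |
|---|---|---|---|---|
| 0.10 | 0.050 | ±0.097 | 4% | 9% |
| 0.20 | 0.066 | ±0.130 | 12% | 26–27% |
| 0.30 | 0.076 | ±0.149 | 18% | 36% |

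The probabilities come from binomial simulation. Stratification by sex and setting is ignored.

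**Step 2: effect on the hazard ratio.** To a first approximation, a difference Δ in prevalence multiplies the hazard ratio by exp(Δ × ln HR_d).

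- Δ = 0.10, HR_d = 3: exp(0.10 × 1.099) = 1.12.
- Δ = 0.10, HR_d = 2: exp(0.10 × 0.693) = 1.07.
- Δ = 0.10, HR_d = 1.5: exp(0.10 × 0.405) = 1.04.
- At the 95% limit with p = 0.20 and HR_d = 3: exp(0.130 × 1.099) = 1.15.
- At the 95% limit with p = 0.30 and HR_d = 3: exp(0.149 × 1.099) = 1.18.

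Cox simulations with onset grouped to two-day visits and HR_d = 3 agree. The slope of the log HR on the prevalence difference was about 1.0 to 1.5 without a diarrhoea term (a slope of 1.3 gives exp(0.13) = 1.14 per 10 points) and near 0 with one.

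**Step 3: set against sampling error.** Simulated SDs of the log HR for one product versus control were about 0.35 with roughly 36 events and 0.6 with roughly 15. The 95% limits are then exp(1.96 × 0.35) = 2.0 to exp(1.96 × 0.6) = 3.2 either side. A shift of 1.04 to 1.18 is small against that.

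**Step 4: what adjustment does not do.** Across the simulated scenarios the spread of the log HR did not narrow (for example 0.353 versus 0.353, and 0.400 versus 0.411 with the term). Changes in power ranged from about −0.5 to +5 points depending on the assumptions. With a true hazard ratio of 1, the mean log HR was 0.00 to 0.01 with or without the term. Ward frailty, sex and setting were not simulated.

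**Step 5: precision of an arm-by-diarrhoea estimate.** At p = 0.20 there are 0.20 × 73 ≈ 15 participants with diarrhoea per arm. If 14-day control risk without diarrhoea is 20% to 30%, the cumulative hazard is −ln(0.8) = 0.223 to −ln(0.7) = 0.357. Multiplying by 3 × 0.5 gives 0.335 to 0.535, a risk of 28% to 41%, or about 4 to 6 events per product arm. The standard error of the film-versus-gel log HR in that subgroup is then sqrt(1/4 + 1/4) = 0.71 to sqrt(1/6 + 1/6) = 0.58, so the limits are a factor of about 3 to 4 either side.

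**The case against.** The strongest case for leaving the plan alone is that this is a choice among covariates. Urinary tract infection, antibiotics, the Barthel index and care level are also recorded and unadjusted, and the documents give no figure that ranks diarrhoea above them. It is one undefined yes/no item in a population that is entirely stool-incontinent, so it is only a proxy for stool load. The Cox model is not bare either: it carries sex, setting and random effects. All of this is correct. What still stands is that diarrhoea is the only stool-related item in the SAP's baseline list, that the protocol names stool contact as a cause of IAD, and that using the item needs no new data.

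A reader might infer three stronger things that the documents do not support.

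- **Lost power.** The protocol makes no sample size calculation and SAP 7.2.1 plans no confirmatory test, so there is no power target to miss. The computed gain is a few points at most, and nil in some scenarios.
- **Bias.** Randomisation makes an imbalance random error. The movement of the hazard ratio away from 1 after adjustment is the difference between a marginal and a conditional quantity.
- **An uninterpretable film-versus-gel contrast.** Reapplication after stool belongs to the assigned regimen, and the trial compares regimens, so it does not confound the intention-to-treat comparison. An arm-by-diarrhoea term would not isolate it: the gel is also reapplied after stool in participants without diarrhoea, and the scheduled frequencies differ as well.

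**Conclusion.** The point holds as a minor one. A pre-allocation, plausibly prognostic variable that the trial already collects is absent from every model, so a chance imbalance would go uncorrected in hazard ratios meant for planning. If diarrhoea triples the hazard, each 10-point difference moves a hazard ratio by a factor of roughly 1.1 to 1.15, and adjustment removes most of that. With a weaker association (hazard ratio 1.5 to 2) the shift is 1.04 to 1.07. At 20% prevalence, a given pair of arms would differ by 10 points or more in about 12% of trials. Prevalence and strength of association are assumptions throughout. The plan's intention-to-treat contrasts remain valid without the change.

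**What to change.** In SAP 7.2, before unblinding, name Day 0 diarrhoea (dm_0120) as a prespecified fixed effect in the IAD Cox model and in the erosion and maceration models. State that Unknown is treated as missing and handled by the multiple imputation that SAP 5.1 already provides for covariates. Add a rule that, if events are too few to support the extra term, the diarrhoea-adjusted model is reported as a prespecified sensitivity analysis beside the planned one. Do not substitute the diary counts of stool episodes, because they arise after allocation.

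Optionally, SAP 7.3 may add an exploratory arm-by-diarrhoea estimate with a 95% confidence interval, labelled imprecise and not presented as separating the product's effect from that of reapplication.

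The cost is a sentence or two of text and one more parameter per model where events may be limited, with no new data. The reported hazard ratio becomes conditional on diarrhoea, which the report should say. The optional interaction adds two further terms.
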